11.5 Study Days and Assessment Windows

Study days will be numbered relative to the first day of dosing. The start of study (Day 1) will be defined as the date on which a subject takes the first dose of any study medication, as recorded on the CRF. Relative to study start, days will be numbered ...-2, -1, 1, 2, ... with Day -1 being the day prior to the start of study medication (Pre-Dose).

Recorded data will be assigned to evaluation/assessment windows. If more than one clinical evaluation is made within a window for a particular visit, the record with the worst assessment will be used for the assessment in that window.

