4. Neovascularization elsewhere (NVE) greater than ½ disc area with pre-retinal or vitreous hemorrhage
5. Vitreous hemorrhage (VH) requiring treatment that is presumed to be from PDR
6. If none of the above is met, Reading Center confirmation of neovascularization within the 7-field fundus photo area should be obtained prior to initiating treatment whenever possible

Treatment of neovascularization outside of the 7-field fundus photo area without the presence of pre-retinal or vitreous hemorrhage is discouraged (If the Investigator believes treatment for peripheral neovascularization is necessary, the sponsor should be informed prior to initiation).

Treatment for PDR can include:

1. Anti-VEGF IVT
2. PRP / sector Laser photocoagulation
3. Vitrectomy

Treatment for DME in the study eye or qualified fellow eye should not be given unless there is center-involved DME on clinical exam with $\geq 10\%$ increase in CST from baseline and:

1. ≥ 10 letter loss of BCVA at a single visit or
2. 5 to 9 letter loss of BCVA at 2 consecutive visits

Treatment for DME can include:

1. Anti-VEGF or steroid IVT
2. Grid / focal Laser photocoagulation

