### 5.5 Safety Endpoints

Safety endpoints include:

- Incidence and severity of systemic and ocular AEs
- Ocular AEs at Study eyes, all qualified eyes and unqualified fellow eyes during treatment period.
- Shift from baseline in body system assessments for the parameters general appearance, HEENT (Head, Ears, Eyes, Nose and Throat), cardiovascular, respiratory, abdomen/gastrointestinal, musculoskeletal, and dermatologic at week 12, 24, 36, 48.
- Change from baseline in vital sign measurements (SBP, DBP, HR, BMI, Weight and Temperature) at every 4 weeks.
- Change from baseline in ECG parameters (HR, PR, QRS and QTcF) at week 24, 48.
- Change from baseline in clinical laboratory assay results (blood chemistry (at every 4 weeks), hematology (at every 8 weeks), fecal occult blood test (at week 24, 36, 48), and urinalysis (at week 24, 36, 48).
- Mean change from baseline in ETDRS Best Corrected Visual Acuity (BCVA) letter score in the study eyes, all qualified eyes and unqualified fellow eyes at every 4 weeks.
- Proportion of subjects with a loss of ≥15 letters, loss of ≥10 letters and loss of ≥5 letters in BCVA compared to baseline at week 48.
- Mean change from baseline in Spectral Domain Optical Coherence Tomography (SD OCT): Central Subfield Thickness (CST) in the study eyes, all qualified eyes and unqualified fellow eyes at week 12, 24, 36, 48.

- Proportion of subjects with increase of  $\geq 100$   $\mu\text{m}$  and increase of  $\geq 50$   $\mu\text{m}$  SD OCT: CST in the study eyes, all qualified eyes and unqualified fellow eyes at week 48.
- Change from baseline in Intraocular Pressure (IOP), with additional sub-group analysis with baseline IOP  $< 16$  mmHg and baseline IOP  $\geq 16$  mmHg in the study eyes and fellow eyes at week 12, 24, 36, 48.
- Shift from baseline in Slit Lamp Biomicroscopy examination for the parameters Eyelids, Cornea, Conjunctiva, Anterior Chamber, Iris/Pupil and Lens in all qualified eyes and unqualified fellow eyes at week 12, 24, 36, 48.
- Shift from baseline in Dilated Indirect Ophthalmoscopy examination for the parameters Vitreous, Macula, Optic Nerve, and Peripheral Retina in all qualified eyes and unqualified fellow eyes at week 12, 24, 36 and 48.

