### 7.1 Missing Data

Efficacy data related to eye anatomy or visual function that is collected after rescue treatment (i.e., treatment for DME or PDR other than study medication) will be treated as missing data. Unless, otherwise stated, missing data will be handled using the following approach:

- For start date, partial dates will have first day of the month imputed if day is missing, and January of that year will be imputed if month is missing. If both day and month are missing, January 01 will be imputed.
- For end date, partial dates will have last day of the month imputed if day is missing, and December of that year will be imputed if month is missing. If both day and month are missing, December 31 will be imputed.
- Missing data are imputed using Last Observation Carried Forward (LOCF) for all visits except screening/baseline; screening/baseline values are not carried forward.
- For vision related efficacy measurements (Tables 14.2.1.x, 14.2.2.x, 14.2.3.x, 14.2.4.x, 14.2.5.x, 14.2.6.x, 14.2.7.x, 14.2.8.x, 14.2.10.x, 24.2.11.x, 14.2.12.x, 14.2.13, 14.3.12.3, 14.3.13.3, 14.3.14.2x, 14.3.14.5) subjects receiving rescue treatment will be handled differently to reflect their status as a treatment failure and to avoid confounding of the effects of rescue treatment with the effects of study drug. Specifically, last pre-rescue data are carried forward for LOCF analysis. If rescue and DRSS occur on the same day, DRSS from that day is carried forward. For Observed Case (OC) analyses, results post-rescue are omitted, and last pre-rescue data are carried forward. Note that for DRSS scales involving both eyes (Person and Binocular scale) the carry forward rules apply only to the rescued eye in calculation of the combined score.
- Where severity or relationship is missing for adverse events, most conservative imputation will be made.

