### 7.2 Descriptive Statistics

For continuous variables, descriptive statistics will include the number of subjects (n), mean, standard deviation (SD), median, minimum and maximum. Categorical variables will be summarized using absolute and relative frequencies (i.e., counts and percentages). For categorical analyses, eyes that receive rescue therapy will be considered as treatment failures. Safety and PK data will be analyzed as collected.

All efficacy data will be summarized by treatment groups and overall using appropriate descriptive statistics. Summaries will be presented for both the MITT and PP populations, where applicable. Due to the small number of subjects enrolled at each center, all summaries and analyses will be performed using data pooled across centers. Unscheduled data, such as information from unscheduled visits or investigator comments, will be included in the data listings. In general, these data will be excluded from the summary tables unless otherwise specified.

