### **11.1.2 Electrocardiogram (ECG)**

Change from baseline for ECG parameters will be presented along with their associated 95% confidence intervals. Potentially clinically significant findings will also be presented based on the following categories:

- The proportion of patients obtaining treatment-emergent absolute QTcF values  $> 450$  ms and  $\leq 480$  ms;  $> 480$  ms and  $\leq 500$  ms; and  $> 500$  ms.
- The proportion of patients obtaining a QTcF increase from baseline values  $> 30$  and  $\leq 60$  ms; and  $> 60$  ms.
- The proportion of patients obtaining a QRS change from baseline  $> 25\%$  resulting in QRS  $> 120$  ms
- The proportion of patients obtaining a PR interval change from baseline  $> 25\%$  reaching a value  $> 220$  ms
- The proportion of patients obtaining a heart rate change from baseline  $> 25\%$  decrease resulting in a heart rate  $< 50$  beats per minute (bpm) and heart rate change from baseline  $> 25\%$  increase resulting in a heart rate  $> 100$  bpm

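### Two SAP rules, on choice of record and on rescue carry-forward, conflict with Protocol 11.5 and with the SAP's own safety convention, and may understate safety findings

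*SAP*

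**What the plan says.** **Choice of record.** Protocol 11.5 deals with a window that holds more than one clinical evaluation: "the record with the worst assessment will be used for the assessment in that window". SAP 3.3 sets a different order. It takes the scheduled visit belonging to the window; failing that, the record nearest the target day; and in a tie, the one nearer the upper end of the window. SAP 7.2 puts unscheduled data in the listings and then says: "In general, these data will be excluded from the summary tables unless otherwise specified". SAP 1.1 reports no change from the protocol.

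The outputs most exposed are counts of subjects who cross a threshold. SAP 11.1.2 plans "The proportion of patients obtaining treatment-emergent absolute QTcF values" in bands above 450, 480 and 500 ms. SAP 5.5 plans the proportions losing at least 15, 10 and 5 "letters in BCVA compared to baseline at week 48".

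**Rescue.** The relevant bullet in SAP 7.1 opens "For vision related efficacy measurements (Tables 14.2.1.x" and its list of tables ends "14.3.12.3, 14.3.13.3, 14.3.14.2x, 14.3.14.5) subjects receiving rescue treatment will be handled differently". For the listed tables the last pre-rescue value is carried forward in the LOCF analysis. It is also carried forward in the observed-case analysis, where later results are dropped. SAP 7.2 states "Safety and PK data will be analyzed as collected" and gives no exception. The sentence just before it counts rescued eyes as treatment failures in categorical analyses.

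**The concern.** Safety outlier tables exist to catch the few subjects who cross a threshold, and abnormal values are often found or confirmed at unscheduled visits or on repeat tests. Protocol 4.4.1 names hepatotoxicity among the identified risks, and Protocol 9.2.1 foresees repeat ECGs. On-treatment ECGs are scheduled only at Months 6 and 12, so an abnormal tracing between those visits is unscheduled by definition. No exception to the exclusion in SAP 7.2 is written for the ECG categories, the laboratory tables or the letter-loss proportions.

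The rescue rule raises a separate problem. Under Protocol 8.4.3, subjects who stay in the trial after treatment for PDR or DME continue study medication, so on-drug acuity and thickness data after rescue will exist. If the listed 14.3 tables are safety tables, those data would not be used in them. A programmer reading SAP 7.1 and 7.2 together could follow any of three handlings and report different percentages for the same subjects.

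**Working it through.** The plan gives no figure on this point. The check is a comparison of texts, followed by arithmetic on scale.

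**1. Record rule.** Protocol 11.5 (worst record) and SAP 3.3 (scheduled, then nearest) cannot both be followed when a window holds an abnormal unscheduled value and a normal scheduled one. The direction here is fixed: taking the worst of several records can never give fewer abnormal findings than taking one of those records by schedule. SAP 3.3 also sits uneasily with SAP 7.2. The former can select a non-scheduled record when no scheduled visit falls in the window, while the latter generally leaves it out. ECG appears in none of SAP Tables 1 to 4, so for ECG the general exclusion in 7.2 is the only written rule.

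**2. What the 14.3 tables are.** Change in BCVA and change in SD-OCT central subfield thickness (CST) appear in the SAP endpoint lists only in 5.5 (safety). BCVA is also a safety endpoint in Protocol 5.6.3. Neither is among the endpoints in SAP 5.1 to 5.4. It is therefore likely, but not proven, that the 14.3 entries in SAP 7.1 are BCVA and CST safety tables.

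**3. What carry-forward fixes in place.** Under Protocol Appendix B, DME treatment needs center-involved DME, a CST increase of at least 10%, and either a loss of 10 or more ("letter loss of BCVA at a single visit") or a loss of 5 to 9 letters at two consecutive visits. A carried value can therefore be a loss of 5 to 14 letters, which misses the 15-letter row. It can equally be 15 or more, since no upper limit is set. The PDR criteria require no letter loss, so an eye rescued for PDR may be held near baseline. The same-day rule in SAP 7.1 covers DRSS only, so an acuity value taken on the rescue day has no stated handling.

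**4. Three handlings of the 15-letter row at week 48.**

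| Rescued study eye | As collected | Pre-rescue carried forward | Treatment failure |
|---|---|---|---|
| 10 to 14 letters lost before rescue, 15 or more at week 48 | counted | not counted | counted |
| 15 or more lost before rescue, fewer at week 48 | not counted | counted | counted |
| Near baseline before rescue for PDR, 15 or more lost at week 48 | counted | not counted | counted |
| Near baseline before rescue for PDR, fewer than 15 lost at week 48 | not counted | not counted | counted |

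**5. Scale.** With 50 planned per arm (SAP 3), one subject is 1/50 = 2 percentage points. The documents give no rescue rate. If rescue is assumed to affect 5%, 10% or 20% of study eyes, then 50 × 0.05 = 2.5, 50 × 0.10 = 5 or 50 × 0.20 = 10 eyes per arm have later values replaced. If an assumed 10% to 50% of those eyes change 15-letter status after rescue, all in one direction, the proportion shifts by between 0.05 × 0.10 = 0.5 and 0.20 × 0.50 = 10 percentage points. The shift is downward if the changes are losses and upward if they are recoveries. If no eye changes status, the shift is zero. These inputs are assumptions, so the range is not an estimate.

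**The case against.** The strongest reply on rescue is that SAP 7.1 calls every listed table efficacy and SAP 7.2 leaves safety data untouched, so there may be no conflict. Three of the four 14.3 entries are single sub-tables, whereas most of the 14.2 entries are whole groups. That would fit rescue-adjusted versions placed beside as-collected ones. CST also has an efficacy role: the note to file uses thickness above 300 microns and an increase of at least 20% to define progression. This stands as far as it goes. Without the shells neither reading can be proven, and the SAP should say which is meant.

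On unscheduled data, the exclusion is qualified and sits in a paragraph that opens with efficacy. SAP 11.1.2 sets no visit restriction on the QTcF counts. Protocol 11.5 does not name unscheduled visits, though it would cover any that fall in a window. Protocol 10.1.1 makes clinically significant laboratory results adverse events, SAP 11.1.1 tabulates treatment-emergent events, and all data are listed. Important findings would therefore not disappear. But adverse event tables and listings do not replace correct threshold counts, and no exception is actually specified.

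A worst-value summary has its own weakness: Protocol 9.2.1 allows ECG repeats to rule out improper lead placement, so the worst tracing may be artefact. That objection stands and shapes the fix.

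A reader might infer that the SAP removes the data most likely to show harm. The documents do not support this. The rescue rule reaches four 14.3 table entries and not laboratory, ECG or vital-sign data. A pre-rescue value can preserve the deterioration that led to treatment, and later values may show recovery. An eye held at 5 to 14 letters lost is still counted in the 5-letter row, and in the 10-letter row if it has lost at least 10.

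**Conclusion.** The concern holds in limited form and is worth correcting before analysis.

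- **Established from the text:** the worst-record rule of Protocol 11.5 was replaced without being declared, and unscheduled values are in general left out of summary tables. Where such values exist, threshold counts can only be equal to or lower than under the protocol rule.
- **Conditional:** if the 14.3 entries in SAP 7.1 are the BCVA and CST safety tables, carry-forward contradicts SAP 7.2, and the treatment-failure sentence adds a third possible handling. The direction of this effect is open.
- **Not established:** any magnitude. Neither rescue counts nor unscheduled counts are in the documents, and the effect may be zero.

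**What to change.** - State in SAP 7.1 which of the listed 14.3 tables are safety tables. Make all collected data, regardless of rescue, the main analysis for BCVA and CST safety, with the pre-rescue version as a supplement. For that supplement, say which value is carried when acuity or thickness is measured on the day of rescue.
- State in SAP 7.2 that the treatment-failure rule applies to efficacy tables only.
- Add worst post-baseline summaries, including unscheduled and repeat values, for the ECG outlier categories, laboratory abnormalities and 15-, 10- and 5-letter loss. Leave out ECGs documented as technically invalid.
- Keep by-visit means on scheduled records, and declare and justify that remaining departure from Protocol 11.5 in SAP 1.1.

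The cost is SAP wording and a few extra tables. Safety percentages may be slightly higher, and post-rescue acuity and thickness will mix in the effect of the rescue treatment, which is why the pre-rescue version is kept as a supplement.

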#### **5.2 Secondary Efficacy Endpoints**

Secondary efficacy endpoints include:

- Proportion of subjects with a worsening in the study eye DRSS of  $\geq 2$  steps at week 48
- Mean change from baseline in DRSS in the study eye at week 48
- Proportion of subjects with an improvement or worsening in the study eye DRSS of  $\geq 3$  steps at week 48.
- Subjects with criterion step improvement in DRSS at week 48 ( $\geq 2$  steps improvement in the study eye for patients with non-qualified fellow eye and  $\geq 3$  steps improvement on the Person scale for patients with qualified fellow eyes)
- Subjects with criterion step improvement in DRSS at week 48 ( $\geq 2$  steps improvement in the study eye for patients with non-qualified fellow eye and  $\geq 3$  steps improvement on the Binocular scale for patients with qualified fellow eyes)
- Proportion of patients developing center-involved Diabetic Macular Edema (DME) or Proliferative Diabetic Retinopathy (PDR) or PDR-related outcomes during treatment period based on Clinical Data. Due to variation in clinician criteria for reporting DME and PDR adverse events, all events will be reviewed and AEs that were not treated and were not validated in FPRC interpretation of imaging data will be censored from the results.
- Proportion of patients developing center-involved DME or PDR or worsening of  $\geq 2$  steps DRSS at week 48 based on Central Image Reading Center Evaluation
- Primary and secondary assessments in qualified fellow eyes and all qualified eyes (study eyes and qualified fellow eyes).

- Primary and secondary endpoints assessed at week 12, 24 and 36.

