# Note to File

**Clinical Study Protocol AKB-9778-CI-5001: PHASE 2 DOUBLE-MASKED, PLACEBO-CONTROLLED STUDY TO ASSESS THE SAFETY AND EFFICACY OF SUBCUTANEOUSLY ADMINISTERED AKB 9778 15MG ONCE DAILY OR 15MG TWICE DAILY FOR 12 MONTHS IN PATIENTS WITH MODERATE TO SEVERE NON-PROLIFERATIVE DIABETIC RETINOPATHY**

To: Statistical Analysis Plan, Final Version 27Feb2019

Date: 03-Mar-2019

Re: Criteria used to define Progression to Vision-Threatening Complications (DME and/or PDR)

---

Criteria used to define Progression to Vision-Threatening Complications (DME and/or PDR):

Qualified eyes were included as progressors if one or more of the following conditions occurred during the trial:

1. An AE of DME was entered that was either treated or was confirmed by the reading center as having either center involved retinal cyst, center involved retinal edema, center involved subretinal fluid, or central subfield thickness >300 microns.
2. An AE of PDR, NVE, NVD, or vitreous hemorrhage
3. IVT with anti-VEGF therapy or corticosteroid with indication for treatment documented as either DME or PDR
4. PRP, Grid laser, or focal laser with indication for treatment documented as either DME or PDR
5. An increase in central subfield thickness of  $\geq 20\%$  at last observation
6. DRSS score of  $>53$ , indicating PDR, at last observation

AERPIO SIGNATURE

DATE

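### The SAP scores the two-eye Person and Binocular responder endpoints from a rescued eye's carried-forward DRSS but elsewhere calls that eye a failure, and it does not say whether rescue is an event in the DRSS-worsening endpoints

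*SAP*

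**What the plan says.** **Carry-forward rule.** SAP 7.1 opens its list as a default: "Unless, otherwise stated, missing data will be handled using the following approach". For vision-related efficacy tables it says rescued subjects are handled so as to reflect treatment failure, and gives the mechanism: "Specifically, last pre-rescue data are carried forward for LOCF analysis". The observed-case analyses also carry the last pre-rescue value. For the Person and Binocular scales, "the carry forward rules apply only to the rescued eye in calculation of the combined score". Baseline values are never carried forward.

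**Failure rule.** SAP 7.2: "For categorical analyses, eyes that receive rescue therapy will be considered as treatment failures".

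**Endpoints.** SAP 5.2 defines two responder endpoints on combined scales. Subjects whose fellow eye is not qualified need a gain of at least 2 steps in the study eye. The others need at least 3 "steps improvement on the Person scale for patients with qualified fellow eyes", or at least 3 on the Binocular scale in the parallel endpoint. It also lists "Proportion of subjects with a worsening in the study eye DRSS of" at least 2 steps, and a 3-step version.

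**Primary endpoint.** SAP 10.1 and Protocol 11.7 define response as a gain of at least 2 steps without need for PDR or DME treatment in the study eye. SAP 5.1 omits that clause. SAP 10.2 sends dichotomous secondary endpoints to the same approach as the primary.

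**Note to File.** For progression to DME or PDR, a qualified eye is a progressor if, among other criteria, it had "IVT with anti-VEGF therapy or corticosteroid with indication for treatment documented as either DME or PDR".

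**The concern.** The two rules answer different questions, and the SAP does not say which governs a subject-level responder endpoint built from two eyes. SAP 7.2 works per eye; the Person and Binocular endpoints are per subject. SAP 7.1 feeds the rescued eye's carried value into the combined score, so that eye can help to produce a response although SAP 7.2 calls it a failure.

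The situation can arise. Protocol 8.4.3 lets subjects stay on study medication after rescue of a study or qualified fellow eye. Protocol Appendix B says: "Treatment for DME in the study eye or qualified fellow eye should not be given unless there is center-involved DME on clinical exam", and the accompanying conditions concern retinal thickness and visual acuity. DRSS is not among them, so an eye with stable or improved DRSS can be rescued.

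For worsening endpoints the word failure is ambiguous. It could mean that a rescued eye counts as worsened, whereas carry-forward may leave it as not worsened. SAP 6 places the analyses after unmasking, so a rule left open until then would be settled when treatment codes are available.

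A smaller, separate gap concerns missing data. A dosed subject with no post-baseline DRSS has nothing to carry forward, and no passage classifies that subject in the primary analysis.

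**Working it through.** **1. The plan's own figure.** SAP 3.1 claims more than 85% power with 45 evaluable per arm, 30% vs 5%, two-sided Fisher's exact test at 0.05. Exact enumeration gives 86.3%, and 45/0.9 = 50 per arm. Both reproduce. The point does not depend on them.

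**2. Person scale.** Input: the table in SAP Appendix 1, with baseline study-eye levels 4, 5 and 6 as in the SAP's stratification. For a worse-eye level w from 2 to 6 the table follows

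- both eyes equal: Person level = 2w − 1
- eyes unequal: Person level = 2w − 2

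The table below takes every baseline pair with the study eye at least as severe as the fellow eye. It lists the smallest gains (study eye, fellow eye) that produce a Person improvement of 3 or more.

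| Baseline (study/fellow) | Baseline Person level | Smallest sufficient gains | Person level after |
|---|---|---|---|
| 4/4 | 7 | (2,1) or (1,2) | 4 |
| 5/4 | 8 | (2,1) | 5 |
| 5/5 | 9 | (2,1) or (1,2) | 6 |
| 6/4 | 10 | (2,0) | 7 |
| 6/5 | 10 | (2,1) | 7 |
| 6/6 | 11 | (2,1) or (1,2) | 8 |

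Suppose the fellow eye was rescued and its last pre-rescue level was carried forward.

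- *6/4, fellow eye unchanged at 4, study eye 6 to 4.* Levels 4/4 give 2×4 − 1 = 7; 10 − 7 = 3, a responder.
- *6/6, fellow eye carried at 4, study eye 6 to 5.* Levels 5/4 give 2×5 − 2 = 8; 11 − 8 = 3, a responder. The study eye gained only 1 step, and the rescued eye supplies the rest.
- In all six pairs, a 2-step gain in the study eye with a 1-step gain carried in the fellow eye is enough.

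In each case the subject is a responder by the SAP 7.1 score and has a failed eye under SAP 7.2. The Binocular scale shares the rule, but the SAP gives no Binocular table, so its effect cannot be enumerated.

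**3. Do other clauses settle it?** Importing the SAP 10.1 clause through SAP 10.2 removes subjects with a rescued study eye from response. It does not reach a rescued qualified fellow eye. Applied to a worsening endpoint, a condition of no need for treatment would take rescued subjects out of the event count, the opposite of failure.

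**4. Worsening endpoints, illustration only.** The counts are assumed. The starting placebo count of 6/50 = 12% is set near the 12.4% two-year sham rate in Protocol section 4, which comes from trials in DME. Two-sided Fisher, 50 per arm:

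| Placebo vs active events | p |
|---|---|
| 6 vs 1 (rescue not an event) | 0.112 |
| 8 vs 1 (rescue adds 2 and 0) | 0.031 |
| 9 vs 2 (adds 3 and 1) | 0.051 |
| 10 vs 2 (adds 4 and 1) | 0.028 |

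One subject is 1/50 = 2 percentage points. A handful of rescued eyes could matter, but the documents do not say how many to expect.

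**5. Missing DRSS in the primary analysis.** As an upper bound, take the whole 10% allowance, 5 per arm, as unclassified. With balanced loss, 13/45 vs 2/45 gives p = 0.0035; counting the missing as non-responders, 13/50 vs 2/50 gives p = 0.0038. With all five on active and none on placebo, 10/45 vs 3/50 (p = 0.034) becomes 10/50 vs 3/50 (p = 0.071).

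**The case against.** **A coherent reading exists.** SAP 7.2 speaks of eyes, and the two-eye sentence in SAP 7.1 is the more specific rule. One could apply failure status to eye-level endpoints and carry-forward to combined scores. This has force: every Person or Binocular endpoint in SAP 5.2 is a responder endpoint, so if SAP 7.2 always won, the SAP 7.1 sentence would have almost no use in the main SAP. But the SAP does not state this reading, and it lets a rescued eye contribute to success under a rule whose stated purpose is to reflect failure. That both readings are defensible is the reason to state one.

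**SAP 10.2 already points to the primary approach.** True, and it is enough for study-eye improvement endpoints. It does not settle the two-eye or worsening endpoints, as shown above.

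**Missing data are not ignored.** This stands. A reader might infer from SAP 10.1, which names only an observed-case analysis in the per-protocol population, that no planned analysis bears on subjects without a Week 48 DRSS. SAP 10 lists the primary outcome in both MITT and PP, under both LOCF and OC, so some comparison is planned. Protocol 7.6 also asks for end-of-treatment assessments, including fundus photography, at early discontinuation. Subjects with no post-baseline value should therefore be well short of the full 10%, and significance is lost above only when all five fall on active.

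**The worsening counts are invented.** Also true. They show sensitivity, not a forecast, and one of the three scenarios does not cross 0.05.

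**Conclusion.** The point holds as an unreconciled pair of rules on secondary endpoints. For the Person responder endpoint the conflict is demonstrated: a rescued qualified fellow eye can count toward a response that SAP 7.2 would deny to that eye. For the Binocular endpoint the same rule applies, but the size cannot be shown. For the DRSS-worsening endpoints it is a wording ambiguity, which the Note to File resolves only for progression to DME or PDR.

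A reader might infer that the primary result is exposed to carry-forward of rescued responders. The documents do not support that: SAP 10.1 and Protocol 11.7 already make a rescued study eye a non-responder, and the ultra-wide field photography plan repeats the clause for its own study-eye endpoint.

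The number of subjects affected is unknown because no rescue rate is given. The endpoints concerned carry no multiplicity adjustment. The unclassified subjects in the primary analysis are a minor addition; balanced loss hardly changes the result. The point should be fixed because the repair is cheap and is best made before treatment codes are known.

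**What to change.** Before unmasking:

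1. In SAP 7.1, state that the SAP 7.2 failure rule takes precedence in every responder analysis. A subject with a rescued contributing eye is then a non-responder whatever the carried value. Contributing means the study eye and, on the Person and Binocular scales, also the qualified fellow eye. The same sentence should cover the secondary Person and Binocular analyses in the ultra-wide field photography plan. Carry-forward then serves only score and mean-change summaries.
2. For each DRSS-worsening endpoint, state whether rescue counts as an event.
3. Add the no-rescue clause to SAP 5.1, so that it matches SAP 10.1.
4. Keep LOCF primary. Beside the MITT LOCF and OC runs in SAP 10, add one MITT sensitivity analysis of the primary endpoint that counts dosed subjects without a Week 48 DRSS as non-responders, including those with no post-baseline value.

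The cost is SAP wording, one derived rescue flag and one table. Response rates may be slightly lower in any arm. For the added analysis, with 10% missing counted as non-responders, the rates become 0.9 × 30% = 27% and 0.9 × 5% = 4.5%. Exact power at 50 per arm is then 84.7%, against 86.3% for 45 evaluable per arm.
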